9.5 Data Analyses

9.5.1 Analysis of pilot/feasibility outcomes

We will use simple descriptive statistics (counts, ratios, mean/standard deviation, median/interquartile range, dispersion, proportions) to analyze the following outcomes: rate of enrollment and percent of eligible participants enrolled, reasons for non-enrollment, proportion of participants completing all visits, proportion of missing data, time to complete study evaluation and instruments, participant satisfaction.

To determine whether any study instruments are redundant and can be eliminated, we will run a series of linear regressions with one instrument score as the dependent variable and the other instruments and demographic variables as independent variables. This would take the form of the following, for example, where the Confusion Assessment Method (CAM) is the dependent variable for the first regression then becomes an independent variable for the second regression (and the FRAIL score becomes the dependent variable):

Regression 1: CAM =

$$\alpha + \beta_1 \text{demographics (age, comorbidity, gender, race, etc)} + \beta_2 \text{FRAIL} \\ + \beta_3 \text{Katz} + \beta_4 \text{MoCA} + \beta_5 \text{Trail Making} + \beta_6 \text{CERAD} + \beta_7 \text{Pain} \\ + \beta_8 \text{Carolinas Comfort Scale}$$

Regression 2: FRAIL =

$$\alpha + \beta_1 \text{demographics} + \beta_2 \text{CAM} + \beta_3 \text{Katz} + \beta_4 \text{MoCA} + \beta_5 \text{Trail Making} \\ + \beta_6 \text{CERAD} + \beta_7 \text{Pain} + \beta_8 \text{Carolinas Comfort Scale}$$

.
.

.

Additional regressions until all instruments have been tested

This process is repeated until all survey instruments have served as a dependent variable. We will calculate the adjusted R-squared for each regression, and this exceeds 40% (40% of the variance for that instrument is explained by the combination of participant demographics and other instruments), then that instrument is considered redundant and will be eliminated for future participants.²² Standard regression diagnostics will be used and we will consider fractional polynomial modeling of all continuous variables as previously described.³¹

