 - a. Measurement: At each visit, after completing all other study forms and procedures, participants will be asked to complete a brief 10-item Likert-type score to measure overall satisfaction with the study visit and a similar item assessing satisfaction with the time burden of the instruments. Additionally, we will conduct a brief interview with open-ended questions at the end of each visit asking patients to provide any feedback on the study procedures or instruments. These will not be recorded but field notes by the research assistant will be taken.
 - b. Timing: Assessments will occur at each study visit and will be reviewed at the last team meeting of each month.
 - 6) Outcome: Whether survey instruments can be eliminated due to redundancy
 - a. Measurement: To determine whether we can reduce the survey burden by eliminating redundant measures, we will employ methods outlined by Harrell for data reduction.²² Each survey instrument will be evaluated as the dependent variable in a separate linear regression with the scores of all other instruments used as predictors, along with demographic information. The adjusted R^2 (explained variance) for each regression will be estimated. Any instrument where the R^2 exceeds 40% will be eliminated based on the idea that little additional information is provided by including that instrument (i.e. the other surveys explain a substantial portion of the information contained within that instrument).
 - b. Timing: We will assess survey redundancy once 25% of planned enrollment is achieved and we will measure again at 75% enrollment. This will provide reasonable data stability for estimation and also provide time for us to test study procedures after eliminating any instruments that are found to be redundant.
 - 7) Outcome: Estimating sample size for fully powered trial
 - a. Measurement: For continuous variables, we will estimate means and standard deviations. For categorical variables, we will estimate proportions and 95% confidence intervals.
 - b. Timing: Final sample size estimate will be performed after data collection for the last patient is complete.

Table 2. Analysis of primary (pilot) outcomes		
Outcome	Measurement	Timing
Rate of enrollment and percent of eligible patients enrolled	
 Running count and graph of planned versus actual enrollment 	Team meeting (every other week)

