 - i. Confusion Assessment Method (CAM) short form: The CAM is the most widely used instrument for detection of delirium, with typical sensitivity of 94% and specificity of 89% across multiple studies.²⁶ The instrument is scored on a 7-point scale and we will consider a 0.5 standard deviation difference as the minimal clinically significant difference.²⁴ Items include evaluation of attention, disorganized thinking, and altered levels of consciousness.
 - ii. Montreal Cognitive Assessment (MoCA) 5-minute form: The MoCA is a widely used tool for detection of dementia and other cognitive impairment, and is sensitive when used as a global cognitive screening tool.²⁷ The 5-minute form was developed to (1) reduce the significant time burden of the longer version which typically takes 15 minutes to complete, while (2) maintaining the psychometric advantages of the longer form, and (3) facilitating assessment by

telephone rather than in-person interviews. The instrument evaluates memory/attention, language fluency, orientation, and recall. The 5-minute MoCA has strong correlation with the full version ($r=0.87$), maintains the discrimination of the full version (area under the curve 0.78 versus 0.75 for full version, $p>0.05$), and has strong test-retest validity (intraclass correlation coefficient 0.89).²⁷ Since the 5-minute MoCA was also developed for testing by phone or in person, it meshes with our protocol plans to conduct immediate and long-term follow up by phone. A difference of 3 points is typically considered clinically significant.²⁷

- iii. Trail Making Tests Parts A and B: The Trail Making Test is one of the most popular neuropsychological tests for detecting processing speed, attention, and visual scanning.²⁸ Part A requires participants to draw a line between circles containing numbers, and the circles must be connected in numerical order. Part B is similar, but alternates letters and numbers (1, A, 2, B, et). Both items are scored as time to completion and then normalized to population data based on age and education.²⁸ To address ceiling effects on Part B, we will use the efficiency score for individuals who do not complete the instrument in <300 seconds.²⁹ A 0.5 standard deviation difference in time is considered clinically significant.²⁸
 - b. Timing: All measures will be administered at baseline, prior to discharge, at 48 hours after discharge, at 2 weeks after surgery, and at 6 months after surgery
- 4) Outcome: Pain

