- a. Measurement: We will use a 10-point visual analog scale to measure overall pain levels. A 0.5 standard deviation will be considered a clinically significant difference.
 - b. Timing: Overall pain will be measured at baseline, prior to discharge, at 48 hours after surgery, at 2 weeks from surgery, and at 6 months from surgery.
- 5) Outcome: Postoperative complications
- a. Measurement: All complications will be recorded based on VA Surgical Quality Improvement Program definitions.³⁰ For complications not defined in VASQIP, definitions are also provided below.
 - i. Allergic reaction: if patients develop hives (raised red lesions) or a significant and persistent rash after administration of local or general anesthesia, this will be managed per the usual hospital protocol. Patients will receive a combination of epinephrine, corticosteroids, and antihistamines. Any patient with an allergic reaction will also be admitted for 24 hour observation that includes monitoring of vital signs, and blood pressure support with intravenous fluids. If the allergic reaction occurs during the operation, then the surgery will be canceled along with all assessments and will be rescheduled after it is determined that the operation can be performed safely without the allergic reaction.
 - ii. Hematoma or seroma: a collection of fluid in the tissues over the

incision site or in the scrotum that is detected on physical exam constitutes either a seroma or hematoma. If minimal symptoms present, this will be managed by observation. If persistent and significant symptoms occur, the seroma/hematoma will initially be managed by aspiration under local anesthesia up to two times. If the symptoms persist after aspiration, then the patient can be taken back to the operating room for surgical evacuation.

- iii. Injury to vessel: during dissection and/or mesh placement, there is the possibility of injury to the femoral or inferior epigastric vessels. If bleeding occurs at these vessels that cannot be resolved by applying pressure, this will be categorized as vascular injury. The inferior epigastric vessel is typically ligated without consequence if injured. Injury to femoral vessels will result in consult to vascular surgery for repair.

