- a. Measurement: Immediately following surgery, patients are typically transported directly to the post-anesthesia recovery unit for close monitoring by nursing staff and anesthesia faculty. Once the effects of anesthesia have diminished and patients are able to stay awake and maintain oxygenation without additional stimuli, they are transported to the stepdown unit for a period of observation to ensure they are able to ambulate and tolerate oral intake without nausea or vomiting. Time in the post-anesthesia care unit will be recorded as the difference between time of transport to the stepdown unit and the time of exit from the operating room. Time in the stepdown unit will be calculated as the difference between the time patients are discharged from the hospital (typically on the same day as surgery) and the time of transport from the post-anesthesia care unit. If patients are admitted rather than being discharged home on the same day as surgery, then stepdown time will be calculated as the difference between arrival in the inpatient or observation unit and the time of entrance to the stepdown unit. All values will be calculated in minutes.
 - b. Timing: These values will be calculated on the day of surgery by research assistants.

Table 3. Analysis of secondary (clinical outcomes)		
Outcome	Measurement	Number of items & time to completion
Quality of life	Carolinas Comfort Scale	8 items Time to completion: 1 minute
Physical function	Katz index	6 items Time to completion: 2 minutes
Cognitive function	1) Confusion Assessment Method (short form) 2) Montreal Cognitive Assessment 5-minute form 3) Trail Making Test Parts A and B	1) 4 items, time to completion 5 minutes 2) 8 items, time to completion 5 minutes 3) 2 trails, time to completion 2 minutes
Pain	Visual Analog Scale	1 item Time to completion: 10 seconds
Postoperative complications	VA Surgical Quality Improvement Program definitions	Complications outlined above Assessed by research assistants and not participants
Operative and anesthesia times	Time from anesthesia note	Assessed by research assistants and not participants

Recovery time in post-anesthesia care unit and stepdown unit	Timer by research assistant	Assessed by research assistants and not participants
--	-----------------------------	--

State and define the secondary outcome measures.

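### The 40% redundancy rule has no exception for an outcome's only instrument, so the pilot could stop measuring pain, quality of life or physical function part-way for little time saved

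*Combined protocol and SAP*

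**What the plan says.** Section 9.4.1, outcome 6, regresses each survey instrument on all the others plus demographics. Any instrument above 40% "will be eliminated based on the idea that little additional information is provided by including that instrument". Section 9.5.1 repeats the rule and describes the cut-off as the point where "40% of the variance for that instrument is explained by the combination of participant demographics and other instruments". It states the consequence without qualification: "then that instrument is considered redundant and will be eliminated for future participants". The rule covers the whole battery: "This process is repeated until all survey instruments have served as a dependent variable". The Katz index, pain and the Carolinas Comfort Scale (CCS) are printed as terms in the example regressions. The rule is applied at 25% and again at 75% of planned enrolment.

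In Section 9.4.2 three secondary outcomes each rest on one instrument: quality of life on the CCS, physical function on the Katz index, and pain on a single scale ("We will use a 10-point visual analog scale to measure overall pain levels"). Each has its own hypothesis in Section 9.1.5. Table 3 lists the pain scale as "1 item Time to completion: 10 seconds".

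Two stated aims depend on these data. Section 1.2 expects the pilot to yield effect-size estimates for each key clinical outcome. Section 9.1.4, item 7, hypothesis 2, expects to pick the multisite trial's primary outcome by weighing required sample size against clinical importance.

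**The concern.** The reason given for removal is that the instrument adds little. A cut-off of 40% does not establish that, because more than half of the score's variance may be predicted by nothing else in the battery. Prediction by instruments for other outcomes, or by demographics, is also not the same as having a substitute. If the CCS, Katz index or pain scale crosses the line, nothing is left to measure that outcome.

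The purpose of elimination is to reduce burden, yet the rule never looks at the time each instrument takes. It treats a 10-second item and a 5-minute test alike. Because removal takes effect inside the pilot, a triggered rule would cut short the data on that outcome and leave it at a disadvantage when candidate primary outcomes are compared.

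**Working it through.** **The cut-off.** The documents cite a textbook for the method but give no derivation of 40%, so there is no figure to reproduce.

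**Unexplained share at the cut-off.**
- Unexplained variance = 1 − R² = 1 − 0.40 = 0.60. The rule fires above 40%, so the share is up to just under 60%.
- Residual SD = √(1 − R²) = √0.60 = 0.77 in SD units.
- Section 9.4.2 uses 0.5 SD as the clinically important difference for the CCS, Katz index and pain scale. The prediction error can therefore exceed it. This compares scale only and is not a power calculation.

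**Time at stake (Table 3).**

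| Instrument | Seconds | Share |
|---|---|---|
| Carolinas Comfort Scale | 60 | 6.6% |
| Katz index | 120 | 13.2% |
| Confusion Assessment Method (CAM) | 300 | 33.0% |
| 5-minute MoCA | 300 | 33.0% |
| Trail Making A and B | 120 | 13.2% |
| Pain scale | 10 | 1.1% |
| Total | 910 | |

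- The three sole instruments: 60 + 120 + 10 = 190 s = 3 min 10 s, and 190/910 = 21%.
- The three cognitive instruments: 300 + 300 + 120 = 720 s, and 720/910 = 79%.
- The pain scale is scheduled at five visits (Section 6.1), so removing it saves at most 5 × 10 = 50 s per participant.

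**Precision lost if an instrument is dropped.** Planned enrolment is 80, allocated 1:1. The approximate standard error of a standardised mean difference with n per arm is √(2/n).
- Dropped at 25%: 0.25 × 80 = 20 enrolled, about 10 per arm; √(2/10) = 0.45.
- Dropped at 75%: 0.75 × 80 = 60 enrolled, about 30 per arm; √(2/30) = 0.26.
- Kept throughout: 40 per arm; √(2/40) = 0.22.
- Approximate 95% half-widths: 1.96 × 0.447 = 0.88 SD at 10 per arm, against 1.96 × 0.224 = 0.44 SD at 40 per arm.

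These figures ignore missed visits.

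**Is there a back-up for pain?** Section 9.4.2 lists neuralgia/chronic pain among the complications, defined as pain lasting more than 3 months. The same section codes complications only up to the 2-week visit. It therefore does not replace the scale.

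**The case against.** The strongest reply is that outcome 6 exists to test whether the battery can be shortened, that Section 9.5.1 removes instruments only for later pilot participants, and that no section makes a removal binding on the multisite trial. Sections 1.1 and 9.1.4 also use softer wording, that instruments can be eliminated. The limit to the pilot stands: the harm shown here is to the pilot's own estimates. The softer wording does not help, because it belongs to the hypothesis, while both statements of the decision rule are mandatory.

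Four stronger readings are tempting and are not supported.

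- **That pain will be lost.** The documents give no correlation between pain, or any other instrument, and the rest of the battery. Loss is possible under the rule, not predicted.
- **That the unexplained 60% is all real information.** Section 9.4.2 credits the 5-minute MoCA with "strong test-retest validity (intraclass correlation coefficient 0.89"; at the cut-off that would leave 0.89 − 0.40 = 0.49 of its variance repeatable but unexplained. This covers MoCA only. No test-retest figure is given for the Katz index or the pain scale, and the CCS item kappas are 0.40–0.60 for all but one item. Some of the remainder may be error.
- **That the plan implies a 75% threshold.** The sentence beginning "The 5-minute MoCA has strong correlation with the full version" reports r = 0.87, and 0.87² = 0.76. It compares two forms of one test, and the plan never uses it as a standard for substitution.
- **That relying on a stand-in would multiply the multisite sample size.** For 0.5 SD (80% power, two-sided 5%) 64 per arm are needed. If the effect is attenuated by √0.40 = 0.632, d = 0.316 and 158 are needed. If it acts entirely through the shared part, d = 0.5/0.632 = 0.79 and 27 suffice. The documents do not say which model applies, so no multiplier follows.

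The Table 3 total also needs a caveat. It omits the frailty scale at baseline, the satisfaction scale and the closing interview, and Visit 3 includes neither the CCS nor the Katz index. The 910 s should not be read as a full visit measured against the 30-minute target.

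**Conclusion.** The point holds. As written, the rule requires removal of an outcome's only instrument if its adjusted R-squared exceeds 40%, with up to just under 60% of its variance unexplained and no regard to minutes saved. For the CCS, Katz index and pain scale together the possible saving is 3 min 10 s per visit. The cost, if triggered at the first look, is an effect estimate resting on about 10 rather than 40 participants per arm, with the standard error roughly doubled. That undercuts the effect-size aim in Section 1.2 and the choice of primary outcome in Section 9.1.4.

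This rests on reading both rule statements literally, on 1:1 allocation at each look, and on Table 3's times. How likely the rule is to fire for any of the three cannot be judged from the documents. The point does not depend on a different R-squared threshold. It is a cheap improvement, not a flaw that threatens the pilot.

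**What to change.** In Section 9.4.1 (outcome 6) and Section 9.5.1:

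1. Keep the regressions and report adjusted R-squared for every instrument, with the minutes saved by dropping it alongside.
2. State that an instrument which is the only measure of a listed secondary outcome (CCS, Katz index, pain scale) will not be eliminated during the pilot.
3. Allow elimination only where another instrument for the same outcome remains, as among the cognitive tests.
4. State how the rule treats the frailty scale, which measures no listed secondary outcome, and CERAD, which is printed in the regressions but appears in neither the schedule of evaluations nor Table 3.

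The cost is a change to the rule for one primary outcome: fewer instruments can be dropped, and up to 3 min 10 s per visit of possible saving is forgone. Section 9.4.2 pairs delirium with cognitive function. If the team regards delirium as a separate outcome, CAM is its only instrument, and the time forgone becomes 190 + 300 = 490 s, or 8 min 10 s. No new data collection is needed.

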6.1 Schedule of Evaluations

Study evaluations are outlined in **Table 1** (next page). Laboratory tests are limited to those obtained routinely as part of the preoperative evaluation so no additional labs/blood draws will be required as part of this study.

Assessment	Screening: Visit-1 (Initial Surgery Clinic Visit)	Baseline, Enrollment, Randomization: Visit 1 (Day 0: Initial Clinic Visit)	Treatment Visit 2 (During Surgery)	Treatment Visit 3 (After Surgery & Before Same Day Discharge)	Treatment Visit 4 (48 Hours After Surgery)	Treatment Visit 5 (2-Week Postoperative Visit)	Follow-Up: Final Visit (6- Month Postoperative Visit)
Informed Consent Form	X						
Demographics	X						
Medical & Surgical History	X						
General Physical Examination	X						
Current Medications	X						
Inclusion/Exclusion Criteria	X						
Blood Chemistries		X					
Hematology		X					
Urine Analysis		X					
Vital Signs		X	X	X		X	
Enrollment/Randomization		X					
Physical Function Assessment: Katz Index		X			X	X	X
Delirium & Cognitive Assessment: (1) Confusion Assessment Method short form, (2) Montreal Cognitive Assessment (5 minute version), (3) Trail Making Tests Parts A & B.		X		X	X	X	X
Frailty Assessment: Fatigue, Resistance, Ambulation, Illness and Loss of Weight Scale		X					
Pain Assessment: Visual Analog		X		X	X	X	X
Quality of Life: Carolinas Comfort Scale		X			X	X	X

Total Operating Room Time			X				
Time for Surgery			X				
Time in Post-Anesthesia Recovery Room				X			
Time in Step-Down Recovery Room				X			
Urinary Function/Unplanned Catheterization				X			
Unplanned Admission				X			
Adverse Events			X	X	X	X	X

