9.1.3 Justification for pilot design

The chances of completing a successful multisite randomized clinical trial are increased by testing study procedures and processes on a smaller scale prior to conducting a fully powered trial.^{18,19} This will enable us to identify and address problems prior to initiating the fully powered study. Conducting a pilot study also allows us to test study instruments and potentially reduce the time burden at each evaluation visit by determining whether study measures are statistically redundant (the other measures explain a substantial portion of one measure's variance). Reducing the time burden for participants is an important step to enhance the completeness of data collection by minimizing missing data and reducing withdrawals from the study.

As outlined below and in the attached grant proposal, data from the pilot study will also be used for preliminary estimation of effect sizes for the future randomized trial. As the pilot is, by definition, not fully powered to detect all relevant differences between groups, this analysis is entirely exploratory.

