9.1.4 Primary outcomes and hypotheses

- 1) Outcome: Rates of enrollment
 - a. Hypothesis: Based on our preliminary data, at least 75% of eligible patients will agree to be randomized.
- 2) Outcome: Proportion of participants completing all study visits
 - a. Hypothesis: We will be able to follow 100% of patients up to their 2 week postoperative visit (as essentially all patients keep this appointment in our clinical practice), and we will be able to follow at least 90% of patients at the six month time point.
- 3) Outcome: Proportion of missing data
 - a. Hypothesis: Missing data on study instruments will be <5%
- 4) Outcome: Time to complete study evaluations and instruments
 - a. Hypothesis: Total time to complete each study evaluation will be acceptable to patients and <30 minutes.
- 5) Outcome: Participant satisfaction with study procedures and instruments
 - a. Hypothesis: Overall time burden for instrument completion will be acceptable to patients

- 6) Outcome: Whether survey instruments can be eliminated due to redundancy
 - b. Hypothesis: One or more study instruments can be eliminated (thus reducing the time burden) because the other instruments may predict a substantial portion of variance
- (7) Outcome: Estimate sample size for fully powered randomized trial.
 - a. Hypothesis 1: Using data from the pilot study, we will be able to establish stable estimates of the necessary sample size for a randomized trial.
 - b. Hypothesis 2: We will be able to identify the optimal primary outcome for a multisite randomized trial by balancing the necessary sample size needed to adequately power the study versus the clinical significance of each outcome.

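### The 40% redundancy rule is first applied at 20 patients and removes every flagged instrument at once, so non-redundant instruments can be dropped by chance and both members of a correlated pair can be lost

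*Combined protocol and SAP*

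**What the plan says.** Section 9.4.1 (outcome 6) and section 9.5.1 set out the rule. Each instrument score is regressed on all the other instrument scores plus demographics (age, comorbidity, gender, race and so on), and the adjusted R-squared is read off. Section 9.4.1 says that any instrument whose R-squared "exceeds 40% will be eliminated based on the idea that little additional information is provided by including that instrument". Section 9.5.1 makes the consequence operational: "then that instrument is considered redundant and will be eliminated for future participants".

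The timing is in section 9.4.1: "We will assess survey redundancy once 25% of planned enrollment is achieved and we will measure again at 75% enrollment". The reason given is "This will provide reasonable data stability for estimation and also provide time for us to test study procedures after eliminating any instruments". With 80 patients planned, the looks fall at 20 and 60 patients.

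The repetition described in section 9.5.1 means only that each instrument takes a turn as dependent variable. Neither section states an order of removal, a refit after a removal, an interval for R-squared, or a way to bring an instrument back.

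The result feeds outcome 7 of section 9.4.1, the sample size for the full trial: "For continuous variables, we will estimate means and standard deviations". Section 9.1.4 adds "We will be able to identify the optimal primary outcome for a multisite randomized trial".

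**The concern.** Two separate defects are at issue.

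**Noise at the first look.** Ten or so predictors on 20 patients leave 9 residual degrees of freedom. Adjusted R-squared is centred correctly when there is no association, but its spread is wide enough to cross 40% by chance quite often. The claim of data stability has no figure behind it.

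**All flagged instruments go together.** If two instruments carry much the same information, each predicts the other and both exceed 40%. The rule then removes both, although the reason for removing one is that the other remains. More patients do not cure this.

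What is at stake is primary outcome 6 itself and, through it, primary outcome 7. The hypothesis in section 9.1.4 that one or more instruments can be eliminated could look confirmed when nothing is redundant. An instrument dropped at 20 patients has post-operative data from only about 20 patients, and the 75% look cannot re-test it in patients who never completed it. Quality of life, physical function and pain rest on one instrument each (Table 3), so they are the most exposed. Operative time, recovery time and complications are unaffected.

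**Working it through.** The plan gives no error rate or stability figure for this rule, so there is none to reproduce.

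**Inputs from the documents**
- Looks at 0.25 × 80 = 20 and 0.75 × 80 = 60 patients (sections 9.2.1 and 9.4.1).
- Seven scheduled instruments: CAM, MoCA, Trail Making (one term, as section 9.5.1 writes it), FRAIL, Katz, pain and Carolinas Comfort Scale. Only baseline has all seven, because "Frailty Assessment: Fatigue, Resistance, Ambulation, Illness and Loss of Weight Scale" is marked at that visit alone (section 6.1).
- Four named demographics (section 9.5.1).

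**Assumptions**
- Normal scores, one row per patient, one degree of freedom per demographic. Each model then has k = 6 + 4 = 10 predictors.
- Correlations between instruments are not given, so a range is shown.

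**Step 1: chance for one unrelated instrument.** Adjusted R² > 0.40 means R² > 1 − 0.6(n − k − 1)/(n − 1). With no association, R² follows Beta(k/2, (n − k − 1)/2).
- n = 20, k = 10: R² must exceed 1 − 0.6 × 9/19 = 0.716; probability 11.7%.
- n = 20, other k: 7.3% with 8 predictors, 14.3% with 11 (CERAD counted), 17.3% with 12.
- n = 18, k = 10, if two records are incomplete (section 9.5.3 uses complete cases): 16.3%.
- n = 60, k = 10: about 0.006%.

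**Step 2: chance that at least one of seven is dropped** (simulation, at least 8,000 runs per case). With all pairs correlated r, the true R² is 6r²/(1 + 5r), below 40% in every row, so no instrument is redundant by the plan's own threshold.

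| Common r | True R² | n = 20 | n = 60 | n = 80 |
|---|---|---|---|---|
| 0 | 0% | 46% | <0.1% | – |
| 0.1 | 4% | 52% | 0.3% | about 0% |
| 0.2 | 12% | 64% | 4% | 0.8% |
| 0.3 | 22% | 77% | 25% | 14% |

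For r = 0 at n = 20, the figure is 31% with two demographic terms and 59% with six. Repeat runs differ by about a percentage point. Counting CERAD as an eighth instrument gives 55%.

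**Step 3: correlated pair, the other five unrelated.** One instrument alone explains r² of the other, so both exceed 40% once r > √0.4 = 0.632. Chance that both are dropped:

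| Pair r | n = 20 | n = 60 | n = 80 |
|---|---|---|---|
| 0.5 | 19% | 5% | 4% |
| 0.6 | 31% | 27% | 26% |
| 0.7 | 54% | 74% | 79% |
| 0.8 | 81% | 99% | >99% |
| 0.7, remove highest and refit | 2% | 0% | 0% |

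Refitting does not change the 46% in step 2: the first removal happens whenever any instrument is above 40%.

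**Step 4: effect on outcome 7.** The 95% limits for an SD are √(df/χ²), with df = patients − 2 for two arms. Required sample size scales with SD².
- 20 patients (df 18): SD 0.76 to 1.48 times the estimate; sample size 0.57 to 2.19 times, a 3.8-fold range.
- 60 patients (df 58): sample size 0.72 to 1.49 times, 2.1-fold.
- 80 patients (df 78): sample size 0.75 to 1.41 times, 1.9-fold.

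The 95% half-width for a difference in means is t√(2/m) SD with m per arm: 0.94 SD for m = 10, against 0.45 SD for m = 40.

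**The case against.** The strongest points on the other side are these.

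- **The cited method is not visible.** Both sections cite a regression textbook, which may describe stepwise removal. That cannot be checked here. But the protocol writes the rule out in full and gives no such step, so staff following the text would drop every flagged instrument. If a sequential step is intended, it needs to be written.
- **The correlations are unknown.** The double drop is likely only for a strongly correlated pair; at r = 0.5 and 60 patients it is 5%. This stands: the possibility is certain, its probability in this trial is not.
- **The 46% counts all seven instruments.** FRAIL is baseline-only and is not a secondary outcome, and cognition has three measures. For quality of life, physical function and pain alone, the chance of losing at least one is about 28% for unrelated instruments (18% with two demographic terms, 40% with six). That is the fairer figure for the downstream harm, and it is still large.
- **Waiting until 60 may be more than needed.** For unrelated instruments the any-drop rate is already 12% at 30 patients and 2% at 40. With mild correlation, though, even 60 is not generous.
- **The harm is bounded.** Section 9.1.3 says of the effect-size estimation that "this analysis is entirely exploratory". Section 9.2.2 draws on published data for the quality-of-life scale and accepts a bootstrap SD range of 42 to 113 minutes for time. These points limit the harm but do not touch primary outcome 6.
- **Early elimination is deliberate.** It gives time to try the shorter battery. That is a real trade-off, taken up under the fix.

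**Conclusion.** The concern holds on both counts. At 20 patients the rule cannot separate redundant from unrelated instruments: about 46% of trials would drop at least one of seven unrelated instruments (31% to 59% across two to six demographic terms), and more if the instruments are mildly correlated. Separately, removing all flagged instruments at once can discard both members of a pair correlated above about 0.63, and above that value this becomes more likely as patients accrue.

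The exact percentages rest on normal scores, one baseline record per patient and assumed correlations. Several of these scores are counts or short scales, so the figures are indicative. The direction does not depend on those details. Because redundancy and sample-size estimation are primary outcomes of this pilot, the rule should be changed before the first look is acted on.

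**What to change.** Change sections 9.4.1 and 9.5.1 and Table 2 as follows.

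1. Make the 25% look report-only.
2. Take any elimination decision at the 75% look already planned (60 patients), or at the end of the pilot.
3. At that point remove only the instrument with the highest adjusted R-squared above 40%, refit the rest, and repeat until none exceeds 40%.
4. Report each adjusted R-squared with an interval and state beforehand how the interval enters the decision. At common r = 0.3, 25% of trials would still drop an instrument at 60 patients on the point estimate alone.
5. As clarifications, name the visit that supplies the scores (baseline is the only one with every scheduled instrument), and reconcile CERAD, which is in the section 9.5.1 models but not in the section 6.1 schedule.

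Steps 1 to 3 are needed together: refitting does not cure chance drops at 20 patients, and a later look does not cure double drops.

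No patients or visits are added. The full battery stays for patients 21 to 60. The Table 3 instruments take about 1 + 2 + 5 + 5 + 2 + 0.2 = 15 minutes, within the under-30-minute hypothesis of section 9.1.4. With a decision at 60, a shortened battery is tried in the last 20 patients rather than the last 60, so the aim of testing it within the pilot is reduced but kept. Deciding only at the end would give that aim up.
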